### 9.3 Analysis Population

The analysis population will be comprised of the results from 141 treated subjects. Results will be presented based on two populations:

*Intention to Treat* (ITT): defined as all enrolled subjects in whom deployment of the Pipeline™ device was attempted. It is possible that the Pipeline™ device may not reach the target site and the **operator** would not attempt to deploy it, in the rare event that happens, that subject will not be considered part of the ITT population.

*Full Analysis Set* (FAS): defined as a subset of ITT including only those in whom the Pipeline™ device was implanted.

*Per protocol* (PP): defined as all enrolled subjects, had the Pipeline™ device implanted, and were followed without any major protocol deviations.

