### **5.4 Procedure**

Subjects must undergo the device placement procedure within 60 calendar days of completion of all baseline assessment tests and procedures. The status of the target IA may change between the screening evaluation and the procedure that may change the risk profile of the study procedure.

Therefore, a pre-treatment (baseline) angiogram will be required before the procedure to confirm that the study procedure can be safely carried out and to collect precise images for the core laboratory. If in the unlikely event that the subject is deemed to be ineligible, the subject will not require any study follow-up.

Each subject will undergo a neurologic examination and assessment using NIHSS. The subject will be tested for antiplatelet response (e.g. using VerifyNow (Accumetrics)). Periprocedural heparin per institutional protocol is required. Prior to inserting the study device, the activated clotting time (ACT) should be checked and adjusted as clinically appropriate. Further ACTs will be checked per standard practice.

The physician will place and deploy the appropriate number of Pipeline™ device braids at the target site to treat the IA.

Post-treatment, the investigator will assess device occlusion, placement and overall status of the aneurysm. Angiograms in the anteroposterior (AP), lateral, and working positions will be obtained. The Investigator will take necessary steps to ensure that pre- and post-placement angiograms are performed using similar views, magnifications, and contrast amount to ensure valid “before/after” comparisons. However, these angiographic details will not be collected in case report forms (CRFs). The Investigator will submit procedural angiograms to the imaging core laboratory. The Investigator will ensure that subject identifiers are removed from all submitted images. Image files/CDs should be labeled with the subject’s study ID number.

Medications appropriate for general anesthesia will be administered using standard hospital practice. Platelet inhibition and aggregations status pre- and post-surgical intervention, including antiplatelet antibodies will be evaluated. All medication use during surgery and immediately post-procedure will be documented. Radiation exposure will be recorded as absorbed radiation dose and cumulative fluoroscopy time will be recorded.

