## **6 ADVERSE EVENTS**

The following adverse events will be collected during the course of the study on the eCRFs.

- All Adverse Events (AE) with an underlying neurological cause (Neurological Adverse Events)
- All Device Related Adverse Events
- All Procedure Related Adverse Events
- All Serious Adverse Events (SAE's)

Adverse event status will be evaluated throughout the study. These will include new events occurring after the point of consent in the study until a subject exits the study. Subjects who are enrolled, underwent surgery to implant to study device but did not have the Pipeline™ device implanted for any reason will be followed for 30 days and relevant safety events will be collected. Investigators must obtain all information available to determine the causality and outcome of the AE and to assess whether it meets the criteria for classification as a serious and/or unexpected event requiring notification to the Sponsor, regulatory agency, and as applicable, IRB/EC, within the specified reporting timeframe. AEs will be categorized using the definitions in **Section 6.1**.

All study AEs, as well as the treatment and follow-up required, should be documented in the subject's medical records and in the eCRF. All study AEs will be followed by the Investigator until resolution or until the end of the 3-year follow-up. A list of potential anticipated adverse events is provided in **Section 10.2**.

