## **9.11 Safety Analysis**

All analyses regarding subject safety will be predicated on the ITT population. The number and proportion of subjects experiencing each type of event will be summarized overall and by site. Only treatment emergent events will be included in the analysis, i.e., events that began or worsened after enrollment.

The safety of the procedure will be measured by the incidence of adverse events. The following sections describe how the safety endpoints will be analyzed.

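### Subjects whose procedure is abandoned before deployment is attempted are in no analysis population, so a stroke caused during access is left out of the 15% safety test

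*Combined protocol and SAP*

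**What the plan says.** **Populations.** Section 9.3 of the combined protocol and SAP, repeated in Section 21, gives three nested or overlapping sets:

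- ITT is "defined as all enrolled subjects in whom deployment of the Pipeline™ device was attempted". The section foresees the case at issue ("It is possible that the Pipeline™ device may not reach the target site") and, where the operator then makes no attempt to deploy, rules: "in the rare event that happens, that subject will not be considered part of the ITT population".
- FAS is "defined as a subset of ITT including only those in whom the Pipeline™ device was implanted".
- PP is "defined as all enrolled subjects, had the Pipeline™ device implanted, and were followed without any major protocol deviations".

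**Analyses that use them.** Section 9.4 first places the primary safety endpoint in ITT and later bases the results on FAS. Section 9.7 tabulates the 30-day endpoint of stroke or neurological death from procedural complications in FAS. Section 9.11 says: "All analyses regarding subject safety will be predicated on the ITT population".

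**Data collected.** Section 6 provides that enrolled subjects who underwent surgery but did not have the "device implanted for any reason will be followed for 30 days and relevant safety events will be collected". Under Section 8.1 the clinical events committee (CEC) reviews all procedure-related adverse events, and Section 9.1 lists all recorded data. Section 5.4 allows a subject not treated at the first session to return, and sets Day 0 to the date of implant.

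**The concern.** Membership of every safety analysis set depends on something that happens during the procedure, and the harm being measured can bring it about. If a vessel is perforated or an embolus occurs while the device is being navigated, the operator may stop. The subject then has the outcome of interest and, because the operator stopped, leaves the analysis.

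The rest of the plan treats such harm as part of the intervention's risk. Section 6.1 classes events from access devices, microcatheters and guidewires as procedure-related. Section 10.2 lists perforation, embolism and stroke among the risks of placement. Section 9.4 justifies the 15% threshold from procedure- or device-related morbidity and mortality with stent-assisted coiling, and describes success in terms of a perioperative rate. A rate without abandoned procedures does not match that rationale. The 30-day endpoint in 9.7 is the one most directly aimed at procedural harm, and it has the same gap.

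**Working it through.** **1. Where the subject falls.** Take a subject with a major stroke during navigation, no deployment attempt and no later implant.

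| Analysis | Set named | Subject included? |
|---|---|---|
| Primary safety test, 9.4 (first statement) | ITT | No |
| Primary safety test, 9.4 (second statement) | FAS | No |
| 30-day procedural endpoint, 9.7 | FAS | No |
| Adverse event tables, 9.11 | ITT | No |
| Supportive per-protocol set, 9.3 | PP | No |
| Individual data listings, 9.1 | All recorded data | Yes |

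The two statements in 9.4 disagree with each other, but settling that disagreement either way does not bring this subject in. If FAS governs, the gap widens: subjects with an attempted but failed deployment also leave the primary test.

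**2. The plan's own figure.** Inputs: threshold 15%, one-sided 97.5% exact Clopper-Pearson limit (9.2, 9.4), n = 141 (9.2, 9.3). The upper limit for x events in n is

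U(x, n) = 0.975 quantile of Beta(x + 1, n − x).

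With x = n × p left fractional, the smallest n with U < 0.15 at p = 5%, 6%, 7%, 8% and 9% is 52, 63, 80, 104 and 141. All five rows of Table 7 reproduce, so this is the test the sponsor has in mind.

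**3. The decision rule in whole events.** U(12, 141) = 14.39% passes and U(13, 141) = 15.25% fails, so the test passes with at most 12 events. At the 9% rate used for the maximum sample size, the expected count is 0.09 × 141 = 12.7, so the boundary lies at the top of the planning range.

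**4. Restoring the excluded subjects.** The plan gives no count of abandoned cases, only that they are rare, so these rows are illustrations.

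| Analyzed under the plan | Abandoned subjects added | Total | Upper limit | Result |
|---|---|---|---|---|
| 12/141 | 1 with event | 13/142 | 15.15% | pass becomes fail |
| 12/141 | 2 with event | 14/143 | 15.88% | pass becomes fail |
| 12/141 | 1 with event, 2 without | 13/144 | 14.94% | stays pass |
| 13/141 | 3 without event | 13/144 | 14.94% | fail becomes pass |
| 6/141 | 1 with event | 7/142 | 9.89% | stays pass |
| 6/141 | 4 with event | 10/145 | 12.32% | stays pass |

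**5. Effect on the false-pass rate.** At a true rate of 15%, P(X ≤ 12 | n = 141) = 1.57%. Now let 15% be the rate over all started procedures, with k abandoned subjects who all have an event and are all left out. The rate among the 141 analyzed is then (0.15 × (141 + k) − k)/141:

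- k = 1: 14.40%, chance of passing 2.5%
- k = 2: 13.79%, chance of passing 3.9%
- k = 3: 13.19%, chance of passing 5.9%

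This is an extreme case. If abandoned subjects have the same 15% rate as the others, the figure stays at 1.57%.

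**The case against.** **Nothing is lost to the study.** A reader might infer that these events are counted nowhere. The documents do not support that. Section 6 collects them for 30 days, the CEC can adjudicate them, serious events are reported to the sponsor, and everything recorded is listed. What is missing is their place in a defined rate or test.

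**The direction is not fixed.** A reader might also infer that the bias can only favor the device. The exclusion removes event-free abandoned subjects as well, and leaving those out raises the rate: 13/141 fails, but with three such subjects restored 13/144 passes. Bias toward the device needs a higher event rate among abandoned cases. That is plausible, because harm can cause the stop, but no figure in the documents establishes it.

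**The result rarely turns on it.** One omitted event reverses the result only at exactly 12 analyzed events. That has probability 4.5% at the 5.6% one-year rate reported for PUFs in Section 1.2.3, and 11.7% at 9%. This stands as a limit on size. It does not justify a rule that drops subjects on an intra-procedural outcome.

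**A returning subject re-enters.** Under 5.4 a subject may be implanted later and so join ITT and FAS. Section 9.11 counts events from enrollment, so first-attempt events would reach its tables. For the primary endpoint this is only a partial answer. Day 0 moves to the implant date, so a first-attempt stroke precedes it and is not clearly a post-procedure event.

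**Section 5.4 against Section 6.** It is tempting to see a contradiction in the rule for the pre-treatment angiogram: "If in the unlikely event that the subject is deemed to be ineligible, the subject will not require any study follow-up". Section 6, however, concerns subjects who underwent surgery to implant the device. The two passages can be read as covering different groups, so this is not part of the point.

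**Adding subjects can dilute the rate.** Never-implanted subjects have 30 days of follow-up, and 9.4 counts non-completers without an event as event-free. This stands, and the fix has to deal with it.

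**Conclusion.** The gap is real and follows from the definitions alone. A subject in whom deployment is never attempted, and who is not implanted later, is outside ITT, FAS and PP. A major stroke or neurological death during access in that subject therefore misses the 15% test, the 30-day procedural endpoint and the safety tables, although the plan already collects the data. If FAS governs 9.4, failed deployments are also missing from the primary test.

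The direction is conditional: the omission favors the device when abandoned cases have more events than the others, and works against it when they do not. The size is small away from the boundary (7/142 has an upper limit of 9.89%). At the boundary it can decide the trial (12/141 passes at 14.39%, 13/142 fails at 15.15%), though two event-free abandoned subjects alongside the one event restore a pass (13/144, 14.94%). These figures assume 141 analyzed subjects and an unknown number of abandoned cases. The point deserves correction because it determines who counts in a primary hypothesis test, not because a large numerical effect is expected.

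**What to change.** 1. In 9.3 and Section 21, define a Safety Population: all enrolled subjects in whom, after eligibility was confirmed, catheterization to place the Pipeline device was started, whether or not deployment was attempted.
2. Use it for the 9.4 safety test, the 9.7 30-day endpoint and the 9.11 tables. Keep ITT and FAS as supportive sets, and remove the conflict between ITT and FAS in 9.4.
3. For a subject brought back and implanted later, state that events from the first attempt onward count in the safety endpoints even though Day 0 is reset.
4. For never-implanted subjects with only 30 days of follow-up, state how they count at 1 year: include their events, and add a sensitivity analysis that leaves the event-free ones out of the denominator so that they do not dilute the rate.

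**Cost.** Protocol and SAP wording, fixed before results are known. No new data collection is needed, because Section 6 already provides the 30-day follow-up. The observed safety rate may become slightly less favorable, and a few subjects will contribute only 30 days to a 1-year endpoint.

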### 9.4 Analysis of the Primary Safety Endpoint and Objective

The primary safety endpoint is the incidence of major stroke or neurological death at 1-year post-procedure in the ITT population. The primary safety objective is to determine if the incidence of major stroke in the territory supplied by the treated artery or neurological death at 1-year of the study procedure is below a pre-specified threshold of 15% with 97.5% confidence.

In the previous Pipeline™ device IDE trial (PUFs), the safety endpoint of occurrence of ipsilateral major stroke or neurological death was evaluated. The most commonly used endovascular approach for small and medium, wide-necked IAs is stent-assisted coil embolization. Published literature on stent-assisted coiling for mainly small and medium wide-necked IAs (Table 1) demonstrates rates of procedure/device-related neurologic deficit ranging from 3.9% to 9.2% and rates of procedure/device-related mortality rates ranging from 0% to 6.8%, yielding combined procedure-/device-related morbidity and mortality rates up to 16%. Although technological advancements have been made, subjects eligible for PREMIER have few reasonable alternatives for sustained occlusion. They face a risk of often-fatal spontaneous bleeding without treatment. They also face a high rate of stroke or death with currently available treatments such as neurosurgery or stent-assisted coiling. A procedure with a high effectiveness rate and perioperative stroke/death rate whose upper confidence limit is <15% represents a significant advance for this patient population. The lack of reasonable alternatives justifies the proposed safety study success parameters.

The 1-sided 97.5% confidence interval will be calculated using the exact Clopper-Pearson method. Results will be based on the Full Analysis Set. Subjects who fail to complete the 1-year post-procedure evaluation period and do not experience the events of interest will be counted as not having experienced the event.

A sensitivity analysis will be prepared using an adjusted analysis model, censoring subjects who withdraw prior to 1-year and did not experience the events of interest.

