To understand the potential effect of a Site effect on the primary performance endpoint, *Site* will be included as a covariate in a logistic regression model, designating the 1 year post-procedure aneurysm occlusion as the dependent variable and calculating the Breslow-Day test of homogeneity of the odds ratios. A probability value less than 0.05 will be considered evidence of a significant difference among the sites. Under this scenario, *Site* would be retained in the model for calculating the adjusted confidence intervals. The intra-site event rate will also be displayed graphically using exact 95% binomial confidence limits.

In the absence of data to suggest otherwise, a subject who does not attend the 1 year post-treatment visit in the allotted time window will not be considered a primary safety endpoint failure unless it is known that the subject experienced stroke or death.

All recorded data will be presented in the individual data listings.

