## 9.2 Sample Size Calculation

Estimates were prepared separately for the primary safety and performance endpoints and based on generating a 1-sided 97.5% Clopper-Pearson exact binomial confidence interval. The upper bound of the confidence interval for safety and the lower bound for performance will be examined relative to the respective *a priori* thresholds. For the primary safety endpoint, the null and alternative hypotheses are as follows:

Ho: Incidence at 1 year post-procedure of major stroke in the territory supplied by the treated artery or neurological death  $\geq 0.15$

Ha: Incidence at 1 year post-procedure of major stroke in the territory supplied by the treated artery or neurological death  $< 0.15$

Reasonable estimates of the observed rate were considered to range between 5% and 9%; the sample size estimates under these scenarios are presented in **Table 7** below:

**Table 7. Observed Incidence at 1 Year Post-Procedure of Major Stroke in the territory supplied by the treated artery or Neurological Death**

Observed Incidence at 1 Year	Minimum Sample Size
5%	52
6%	63
7%	80
8%	104
9%	141

For the primary effectiveness endpoint, the null and alternative hypotheses are as follows:

Ho: Incidence at 1 year post-procedure of aneurysm occlusion without significant parent artery stenosis  $\leq 0.50$

Ha: Incidence at 1 year post-procedure of aneurysm occlusion without significant parent artery stenosis  $> 0.50$

Reasonable estimates of the observed rate were estimates at 61% to 65%; the sample size estimates under these scenarios are presented in **Table 8** below:

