**Table 8. Observed Incidence at 1 Year Post-Procedure of Aneurysm Occlusion Without Significant Parent Artery Stenosis**

Observed Incidence at 1 Year	Minimum Sample Size
61%	100
62%	83
63%	71
64%	61
65%	53

The maximum number of subjects to be enrolled in this clinical investigation will be 141 subjects, based on an incidence at 1 year of major stroke in the territory supplied by the treated artery or neurological death of 9%. Based on the expected incidence of the primary endpoints, a minimum of 80 subjects will be enrolled.

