## 9.5 Analysis of the Primary Effectiveness Endpoint and Objective

The primary effectiveness endpoint is the incidence of aneurysm occlusion without significant parent artery stenosis at 1 year post-procedure without re-intervention in the FAS population. The primary performance objective is to determine if the incidence is above a pre-specified threshold of 50% with 97.5% confidence.

Previously, in the PUFs IDE study, the same effectiveness endpoint of complete occlusion without major stenosis was evaluated. For subject with small and medium wide-necked IAs, treatment options for sustained occlusion are fairly limited. Currently, these IAs are commonly treated with stent-assisted coiling. Published literature on stent-assisted coil embolization has reported an occlusion rate at 1 year post-procedure ranging 46% to 75%. Aneurysm recanalization rates up to 28% have been reported; often requiring the subject to be retreated. Given that these rates represent the effectiveness of the current treatment alternative, a threshold of 50% will be established for the primary effectiveness endpoint.

Primary effectiveness evaluations of occlusion will be assessed by an independent core laboratory. The 1-sided 97.5% confidence interval will be calculated using the exact Clopper-Pearson method. Results will be based on the Full Analysis Set. Subjects who fail to complete the 1-year post-procedure evaluation will be counted as having met the primary performance endpoint.

A tipping point analysis will be performed as a sensitivity analysis for the primary effectiveness endpoint. An additional worst-case sensitivity analysis will be prepared, assuming subjects who withdraw prior to

the 1-year evaluation visit experienced significant stenosis, therefore not meeting the primary effectiveness endpoint.

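### Counting subjects lost before 1 year as event-free can only favour the 15% safety test, and no planned analysis covers loss related to outcome

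*Combined protocol and SAP*

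**What the plan says.** Section 9.4 sets the safety objective as showing that the 1-year incidence of major stroke in the treated territory or neurological death "is below a pre-specified threshold of 15% with 97.5% confidence". It fixes the method: "The 1-sided 97.5% confidence interval will be calculated using the exact Clopper-Pearson method". Results are to be based on the Full Analysis Set (FAS), although the opening sentence of the section names the ITT population.

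For subjects without a full year of follow-up, section 9.4 says that those who "do not experience the events of interest will be counted as not having experienced the event". Section 9.1 repeats the rule for a missed 1-year visit: absent other data, the subject "will not be considered a primary safety endpoint failure unless it is known that the subject experienced stroke or death". Section 9.10 is consistent with both, because it carries the last observed condition forward for the primary endpoints.

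Section 9.4 adds one sensitivity analysis, an adjusted model that censors event-free subjects who withdraw before 1 year. It names no estimator or confidence limit and gives the result no role in the conclusion. For effectiveness, section 9.5 goes further: "A tipping point analysis will be performed as a sensitivity analysis for the primary effectiveness endpoint". It also adds a worst-case analysis.

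**The concern.** The test succeeds when the event rate is shown to be low. A lost subject with an unknown outcome is entered as the favourable one, so the error has a single direction. Each unseen event lowers the count and leaves the denominator unchanged.

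At stake is the primary safety claim on stroke and neurological death. Neurological worsening can itself cause missed visits, so loss may be related to outcome. Censoring assumes that it is not. The plan tests that assumption for effectiveness but not for safety, so a reader of a narrow safety pass could not tell how much it owes to missing follow-up.

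**Working it through.** **Inputs.** Threshold 15% and a 1-sided 97.5% exact bound (section 9.4). The nominal 2.5% error is implied by that bound and is not printed. For the analysis size, section 9.3 says: "The analysis population will be comprised of the results from 141 treated subjects". Section 9.2 ties that number to a 9% rate: "The maximum number of subjects to be enrolled in this clinical investigation will be 141 subjects, based on an incidence at 1 year". Section 9.6 puts about 80% of 1-year events within 6 months. No post-treatment dropout rate is given; the roughly 30% in section 4.1 is screen failure. The loss rates below are assumptions.

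**Reproducing Table 7.** The upper bound is the 0.975 quantile of a Beta(x+1, n−x) distribution, with x = rate × n left unrounded. The smallest n with a bound below 15% is 52, 63, 80, 104 and 141 for 5%, 6%, 7%, 8% and 9%. All five rows match.

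**Decision rule at n = 141.** 12/141 has an upper limit of 14.39% and passes. 13/141 has 15.25% and fails.

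**Error with complete follow-up.** P(X ≤ 12 | n = 141, p = 0.15) = 1.57%. The test is discrete, which leaves a cushion below 2.5%.

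**Breakeven.** P(X ≤ 12) reaches 2.5% at p = 14.39%. Then 1 − 0.1439/0.15 = 4.04% (from unrounded values): about 4% of true events must go unseen.

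**Error under loss, lost subjects at average risk.** Let L be the share lost and f the share of their 1-year risk observed before loss. The observable rate is 0.15 × [1 − L(1 − f)].

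| L | f | Observable rate | Type I error |
|---|---|---|---|
| 10% | 0.8 | 14.70% | 2.0% |
| 10% | 0.5 | 14.25% | 2.8% |
| 20% | 0.8 | 14.40% | 2.5% (2.49%) |
| 20% | 0.5 | 13.50% | 4.7% |

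Put as a loss rate, breakeven is 4.04%/0.2 = 20.2% lost at f = 0.8, or 4.04%/0.5 = 8.1% lost at f = 0.5.

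**Loss spread over the year.** A simulation at a true 15% (20,000 runs, 80% of events in the first 6 months, loss unrelated to outcome) gave 1.6%, 1.9%, 2.4%, 2.8% and 3.3% for the planned rule at 0, 5, 10, 15 and 20% loss. A Kaplan-Meier 1-year rate with a log-log upper limit stayed between 1.4% and 1.8%, including when loss fell in the first 3 months.

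**Loss related to outcome (illustration).** Suppose 10% are lost and carry twice the average risk (30%), with the overall true rate still 15%. The observable rate is 0.15 − 0.10 × 0.30 × (1 − f): 14.4% at f = 0.8 and 13.5% at f = 0.5. The errors are 2.5% and 4.7%, the same as for 20% loss at average risk.

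**Tipping point.** With x observed events, 13 − x of the lost event-free subjects would need to have had an event for the test to fail: 6 if x = 7, and 1 if x = 12.

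**The case against.** The strongest defence has four parts.

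- **Risk is early.** Section 9.6 calls its 80% figure conservative. In the earlier pivotal study of the device (section 1.2.3) the rate was 5.6% at both 180 days and 1 year. With f = 0.8 the error stays within 2.5% up to 20% loss. This stands for late loss. It does not settle the matter, because the 80% says nothing about when subjects leave or whether leavers have average risk.
- **Non-informative loss is already addressed.** Section 9.4 plans a censoring analysis. This stands: a reader might infer that the plan has no safety sensitivity analysis, and that would be wrong. The gap is that the analysis is loosely specified, has no stated role in the conclusion, and cannot speak to loss related to outcome.
- **A missed visit is not a missing outcome.** Section 9.1 counts any known event, section 5.11.3 requires three contact attempts ending with a registered letter, and section 6.2 requests death certificates. These steps should reduce the number of unknowns but do not bring it to zero.
- **The extreme scenario is unrealistic.** Setting f = 0 gives 4.7% at 10% loss and 12.3% at 20%. A reader might quote those figures, but FAS subjects are implanted and have NIHSS and adverse events assessed at the procedure and at discharge. Some of their risk is always observed.

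A reader might also infer that the primary denominator should be limited to subjects with an event or followed to the opening of the 1-year window (day 365 − 42 = 323). That keeps leavers' events and discards their event-free follow-up, so it biases the rate upward. At 10% loss, f = 0.8 and a true 15%, its simulated expected rate is 16.1%, against 14.7% under the plan. At a true 7%, the chance of passing falls from 83% to 70%.

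**Conclusion.** The point holds in a limited form. The rule can bias the safety rate only downward, and the type I error can exceed the implied 2.5%, but only once about 4% of true events go unseen. Under assumed loss of 10% to 20% at average risk, the error is 2.0% to 2.5% if 80% of the lost subjects' risk was observed and 2.8% to 4.7% if half was.

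The documents do not support saying that the test is invalid or that 2.5% will be breached. They give no dropout rate, they place most events early, and the exact test starts at 1.6%. The firm finding is the asymmetry: loss related to outcome is examined for effectiveness and not for safety.

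**What to change.** Keep the exact FAS test as primary, and settle the ITT/FAS wording in section 9.4. Then add to that section:

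1. A safety tipping-point table giving the number of event-free subjects without 1-year follow-up who would need to have had an event for the upper limit to reach 15% (13 events in total at n = 141). Include a worst-case row that counts all of them as events. That row is descriptive: at 10% loss it adds 0.10 × 141 ≈ 14 events and fails by itself.
2. A specification of the planned censoring analysis as the Kaplan-Meier 1-year rate with a 1-sided 97.5% upper limit compared with 15%, reported beside the primary result.
3. A statement that a pass is called robust only if it also holds under the Kaplan-Meier analysis and the tipping point is implausible given the number lost.

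The cost is some SAP wording and one extra table. The primary test and its chance of passing do not change, but a pass near the boundary may have to be described as fragile.
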